7.1.2 Temporary discontinuation

Temporary treatment discontinuation may be considered by the Investigator because of suspected AEs or for other reason.

For all temporary treatment discontinuations, duration must be recorded by the Investigator in the appropriate pages of the eCRF.

7.1.2.1 Rechallenge

In case of treatment interruption due to an AE, reinitiation of treatment with the IMP will be done under close and appropriate clinical/and or laboratory monitoring once the Investigator will have considered according to his/her best medical judgment that the responsibility of the IMP(s) in the occurrence of the concerned event was unlikely and if the selection criteria for the study are still met (refer to Section 5.1 and Section 5.2).

7.2 PARTICIPANT DISCONTINUATION/WITHDRAWAL FROM THE STUDY

- A participant may withdraw from the study at any time at his/her own request, or may be withdrawn at any time at the discretion of the Investigator for safety, behavioral, compliance, or administrative reasons.
- If the participant withdraws consent for disclosure of future information, the Sponsor may retain and continue to use any data collected before such a withdrawal of consent.
- If a participant withdraws from the study, he/she may request destruction of any samples taken and not tested, and the Investigator must document this in the site study records.
- See SoA for data to be collected at the time of study discontinuation and follow-up and for any further evaluations that need to be completed.

If participants no longer wish to take the IMP, they will be encouraged to remain in the study.

The Investigators should discuss with them key visits to attend. The value of all their study data collected during their continued involvement will be emphasized as important to the public health value of the study.

Participants who withdraw from the study intervention should be explicitly asked about the contribution of possible AEs to their decision, and any AE information elicited must be documented.

All study withdrawals should be recorded by the Investigator in the appropriate screens of the e-CRF and in the participant's medical records. In the medical record, at least the date of the withdrawal and the reason should be documented.

In addition, a participant may withdraw his/her consent to stop participating in the study. Withdrawal of consent for intervention should be distinguished from withdrawal of consent for follow-up visits and from withdrawal of consent for non-participant contact follow-up, eg, medical record checks. The site should document any case of withdrawal of consent.

Participants who have withdrawn from the study cannot be rerandomized (treated) in the study. Their inclusion and intervention numbers must not be reused.

7.3 LOST TO FOLLOW UP

A participant will be considered lost to follow-up if he or she repeatedly fails to return for scheduled visits and is unable to be contacted by the study site.

The following actions must be taken if a participant fails to return to the clinic for a required study visit:

- The site must attempt to contact the participant and reschedule the missed visit as soon as possible and counsel the participant on the importance of maintaining the assigned visit schedule and ascertain whether or not the participant wishes to and/or should continue in the study.
- Before a participant is deemed lost to follow up, the Investigator or designee must make
 every effort to regain contact with the participant (where possible, 3 telephone calls and, if
 necessary, a certified letter to the participant's last known mailing address or local
 equivalent methods). These contact attempts should be documented in the participant's
 medical record.
- Should the participant continue to be unreachable, he/she will be considered to have withdrawn from the study.

8 STUDY ASSESSMENTS AND PROCEDURES

- Study procedures and their timing are summarized in the SoA. Protocol waivers or exemptions are not allowed.
- Immediate safety concerns should be discussed with the Sponsor immediately upon occurrence or awareness to determine if the participant should continue or discontinue study intervention.
- Adherence to the study design requirements, including those specified in the SoA, is essential and required for study conduct.
- All screening evaluations must be completed and reviewed to confirm that potential participants meet all eligibility criteria. The Investigator will maintain a screening log to record details of all participants screened and to confirm eligibility or record reasons for screening failure, as applicable.
- Procedures conducted as part of the participant's routine clinical management (eg, blood count) and obtained before signing of the ICF may be utilized for screening or baseline purposes provided the procedures met the protocol-specified criteria and were performed within the time frame defined in the SoA.

8.1 EFFICACY ASSESSMENTS

8.1.1 Continuous glucose monitoring (CGM)

A CGM system is a device that records interstitial glucose levels continuously throughout the day and night via a subcutaneous sensor. During the study, patients will use the Dexcom G6[®] CGM system with software (DexCom, Inc., San Diego, CA), an approved device with single-use disposable electrochemical sensing elements designed for up to 10 days of continuous use with measurement of glucose levels in interstitial fluid in 5-minute intervals.

All patients must use the CGM device provided by the Sponsor during the CGM collection periods. Additionally, patients cannot initiate personal (non-study) real time, flash or implantable CGM system during the study (see E 13).

8.1.1.1 CGM performance

Two (2) sets of CGM will be conducted by the study patients. Baseline CGM will start at Visit 3 (Week -3) and stop at randomization visit (Visit 6). During the randomized treatment period, an endpoint CGM recording during Weeks 9, 10, 11 and 12 [Days 64 to 84]) will be done. Patients must be well trained to understand the importance of the CGM performance and compliance with the manufacture's (DexCom) instructions.

All patients will undergo training, delivered by the investigational site personnel, at Visit 2 regardless of previous experience with CGM. After the training, patients should understand the process of CGM and how to handle the CGM device at home, the distance of receiver and effect of temperature on the device etc. If the patient is not sufficiently compliant with the study procedures, all necessary training has to be repeated by the site staff.

Patients, Investigators, and study personnel will be blinded to the CGM data. The CGM receiver's screen will be blocked of displaying data. Neither patients nor Investigators will be able to see the glucose values.

At Visit 3 and Visit 15, the insertion of CGM sensor will occur under the supervision of Investigators or designees. Patients will be instructed to insert the sensor into the belly (abdomen) at least 8 cm (3 inches) away from the insulin injection sites.

After the CGM sensor being inserted, and the transmitter being attached, patients will stay in the study site as long as needed to explain the use of CGM. During the next 19 days when the patients are operating the CGM, they must:

- Carry the CGM receiver with them all the time; the receiver must be placed within 20 feet (6 meters) from the patients' body in order to capture the data measured by the device.
- After 10 days of wearing the device, patients must remove and replace the sensor themselves. **Note:** If required, Investigators can arrange for patients to attend the site after the first 10 days of CGM for the sensor to be replaced at the study site.

Patients will receive a user guide of instruction included in the DexCom G6 device kit. Technique support via a 24/7 help-line service for trouble shooting will be provided by the manufacturer, DexCom. The patients should immediately contact the sites if they encounter any device malfunction or device related events eg, sensor fracture. The Investigator or a site staff will help patients contact the DexCom service line for problem solving.

After the end of the study, the patients and their Investigator will receive a standardized analysis (eg, Ambulatory Glucose Profile) of their personal two 20-day CGM-periods.

8.1.1.2 CGM qualification and data transfer

CGM qualification

There are 2 periods of CGM in this study. During each CGM period, patients will wear the CGM for 20 consecutive days to generate a minimum of (10 days, not necessarily consecutive) of useable CGM records. Useable CGM data for a day/a 24-hour CGM profile are defined as:

- At least 80% time of records per 24 hours.
- No gap (missing data) lasting for ≥ 2 hours per 24 hours besides the warm-up time for the sensor after insertion.

Note: Only patients with 10 days out of 20 of qualified CGM records will proceed to randomization and other CGM recording periods.

CGM data transfer

The CGM data will be uploaded to a separate server which assures maintenance of the blind with vendor software (QuintilesIMS Study Management Suite) and a data acceptability report with daily CGM performance will be available immediately. This will be performed at the end of the 20-day CGM period and may additionally be generated in the event of a patient returning to the site for replacement of the sensor after the first 10 days of CGM. Investigators will not be able to see the recorded glucose values, nor will the report include any real glucose data. The CGM summary will be used for the Investigators to review the patient's daily performances and determine the quality of CGM and will be considered as source documents).

Use of CGM data for future analysis

After the database lock anonymized CGM data may be transferred to a third party for future analysis and modeling of glycemic values.

8.1.2 Glycated hemoglobin A1c

Glycated hemoglobin A1c is assayed at screening (Visit 1; Week -6/-5), randomization Visit 6 and Visit 18 (Week 12). For the eligibility and efficacy assessments of the study, HbA1c is measured by a certified level I "National Glycohemoglobin Standardization Program", or equivalent certification as per specific country regulations, central laboratory. The screening value will be transferred into the IRT for stratification purpose during the patient randomization at the Visit 6.

8.1.3 Fasting plasma glucose

Fasting plasma glucose is measured at a central laboratory. Blood samples for FPG measurement are taken at screening (Week -6/-5), randomization Visit 6 and at Visit 18 (Week 12).

8.1.4 Self-monitoring of plasma glucose

Plasma glucose values will be self-measured by the patients using the Sponsor-provided glucometers and corresponding supplies (lancet, control solutions, test strips, etc). Patients should not use their own glucometers during the study period starting after Visit 2 (Week -4).

Self-monitoring plasma glucose performance

At Visit 2, the patients will be shown how to accurately measure plasma glucose values with the blood glucometers. The Investigator or a member of the investigational staff will explain the need to measure glucose at the times requested for profiles and how to correctly record the values and times. Training will be repeated as often as necessary at the study visits and the investigational staff will review the study diary at each visit.

The schedule for performing SMPG is specified in Section 1.3.

Self-monitoring of plasma glucose readings will be used to guide the basal and mealtime insulin titration to reach glucose targets. The Investigators should review the SMPG records at each visit and also ask the pattern of fasting and postprandial SMPG so that they can provide instruction to the patients for appropriate insulin dose adjustment. Investigators may request more frequent blood glucose test and/or at specific time eg, midnight, if needed, to help the patients optimize insulin dosage. The SMPG records will be the patient's study diary entries (available at each visit). The SMPG summary report downloaded at Visits 6, 14, 15 and 18 will also be available to Investigators.

Investigators will record SMPG values and insulin doses during weekly telephone contacts as well.

Fasting self-monitoring of plasma glucose

After randomization, before breakfast SMPG = Pre-injection SMPG

Pre-injection SMPG: Within 30 minutes prior to injection of Toujeo or Tresiba before breakfast on the day of the first injection of the IMP (Day 1/Visit 6) and daily until uptitration has been completed and fasting pre-breakfast SMPG is stable in the target range, and then, at least 3 fasting measurements per week.

2 hours PPG will be measured by patient regularly as instructed by investigator to guide the dosing of meal time insulin.

7-point SMPG profiles

Before (pre-injection after randomization) and 2 hours after breakfast; lunch; dinner, and at bedtime: at least 1 day during the week that precedes Visits 6 and 18. Note: 7-point SMPG profile should also be pre-injection during the run-in period in cases where the patient's current basal insulin is administered in the morning.

SMPG during symptomatic hypoglycemia

Whenever the patients feel hypoglycemic symptoms, plasma glucose should be measured by the patient (or others, if applicable), if possible. Patients should be instructed to self-assess plasma glucose levels prior to carbohydrate intake/administration of glucose whenever symptomatic hypoglycemia is suspected, unless safety considerations necessitate immediate carbohydrate/glucose rescue prior to confirmation with the SMPG.

Patients have to document hypoglycemic events appropriately in their diaries and contact the Investigator as soon as possible following severe events for review and for decision on any necessary actions to be taken.

All hypoglycemia episodes will be documented on the "hypoglycemia specific form" in the eCRF. This includes all symptomatic hypoglycemia events and asymptomatic hypoglycemia. Investigators should review the SMPG diary entries (and when available also data stored in the glucometer) to assess data for episodes of hypoglycemia, ie, to confirm episodes reported by patients in the diary and also to identify any episodes that were not reported in the diary).

Property of the Sanofi group - strictly confidential

Page 49

Hypoglycemia events fulfilling the criteria of a SAE will also be documented on the AE and SAE form in the eCRF.

Recording of SMPG data

Patients will document their SMPG values with the testing times in the Sponsor-provided diary. If for any reason, SMPG is recorded by the patient in a non-Sponsor provided diary, the Investigator (or designee) and patient will sign/initial the data so that the diary can be kept in the study source documents.

At on-site Visits 6, 14, and 18, SMPG data stored in the individual's glucometer will be uploaded to the site's computer. A summary including all measured glucose values will be promptly available for the Investigator (or designee) to review. SMPG data will be uploaded to site's PC (server independent from eCRF). At a minimum, for SMPG data that are captured in the eCRF, including the values recorded during weekly telephone contacts, the Investigators or study staff must verify the accuracy with the data that are uploaded from the glucometer. Once an error is identified, only the corrected data should be entered in the eCRF and erroneous data in the diary will be corrected by the patient and initialed.

Use of SMPG data for future analysis

The SMPG data from the glucometer will be uploaded to an independent server and will not be captured in the clinical database (which will comprise SMPG data that is transcribed from the study diary).

The downloaded SMPG data will not be analyzed or reported in the clinical study report.

After the database lock anonymized SMPG data may be transferred to third party for future analysis and modeling of glycemic values.

8.1.5 Insulin dose (including IMP during the treatment period)

Insulin dose and injection time for both basal insulin (ie, patient's current basal insulin prior to randomization or IMP [Toujeo or Tresiba] after randomization) and mealtime insulin will be documented in the study diary on a **daily basis**. All doses of mealtime insulin analog during the day as taken for all meals and all snacks must be recorded.

- At Weeks 4, 8, and 12, the following data will be entered in the eCRF:
 - The dose the patient was taking prior to the visit and the dose taken after the visit (so as to reveal any dose adjustments made at the visit),
 - All available data on the injection time and doses administered will be entered in the eCRF, 1 week before on site visit, including missed injection,
 - Missed injections.
- In case of symptomatic hypoglycemia, the dose and injection time should be entered in the eCRF on the specific hypoglycemia form.

- All available data of dose and injection time on the last 3 days before permanently IMP treatment discontinuation.
- Data on SMPG values and dose of basal and rapid acting insulin, obtained verbally during weekly telephone contacts.

8.1.6 Patient-reported Outcomes (PROs)

The patient-reported outcome (PRO) questionnaires in this study are the Treatment Satisfaction Questionnaire (DTSQs and DTSQc versions), the MOS Sleep and the Work Productivity and Activity Impairment Questionnaire (WPAI).

The patients will be requested to complete all the questionnaires by themselves during selected clinical visits (see study SoA), independently from investigator, site staff and any help from friends or relatives. For validity purposes, patients will be asked to answer all the questions of the questionnaires at the start of the visit in a quiet place, and while on site to return the completed questionnaires on the same day.

In case of premature discontinuation of study treatment, all the PRO questionnaires will be completed by the patients as normally planned at 12 weeks.

8.1.6.1 DTSQs

8.1.6.2 DTSQc

The Diabetes Treatment Satisfaction Questionnaire Status Version (DTSQs) will be used to evaluate patient satisfaction with treatment and patient perception of blood glucose control over a several week period (16). The DTSQs is a validated questionnaire comprised of 8 questions which are answered on a Likert scale from 0 to 6. Responses to 6 of the items will be summed to produce a Total Treatment Satisfaction score ranging from 0 (no satisfaction) to 36 (high satisfaction with treatment). The 2 items of 'perceived frequency of 'hyperglycemia' (Item 2) and 'perceived frequency of hypoglycemia' (Item 3) are scored separately ranging from 0 (none of the time) to 6 (most of the time). The DTSQs will be completed by the patients at baseline and Week 12. Mean differences in scores from baseline and between groups will be evaluated to understand the impact of treatment on patient satisfaction.

The DTSQs is available in appendix 5 (Section 10.5).

The Diabetes Treatment Satisfaction Questionnaire Change Version (DTSQc) was developed from the original DTSQ to evaluate the change in treatment satisfaction at a specific time point. The DTSQc instructions and response options differ from those of the DTSQs to produce measures of relative change in satisfaction rather than measures of absolute satisfaction.

It will be used to measure patient perception of change in treatment satisfaction at 12 weeks. Scores for DTSQc treatment satisfaction items range from -3 to +3, and the sum of the treatment satisfaction score range from -18 to +18. Positive scores are indicative of improvement in treatment satisfaction, whereas negative scores are indicative of deterioration in treatment satisfaction since start of the study. Perceived frequency of hyperglycemia and hypoglycemia

scores range from -3 to +3, with negative scores indicating fewer problems with blood glucose levels and positive scores indicating more problems than before. DTSQc will be completed by the patients at 12 weeks after the DTSQs (status version). To control for baseline scores, DTSQs will be used as a measure of treatment satisfaction at baseline.

The DTSQc is available in appendix 5 (Section 10.5).

8.1.6.3 MOS Sleep

Originally developed for use in the Medical Outcomes Study (MOS), the MOS Sleep Scale is a brief, self-administered generic assessment designed to measure key aspects of sleep, such as disturbance, adequacy, somnolence, and quantity.

The 12-item acute revised version of the MOS Sleep will be used in this study with a past week recall period and 5-point likert response options (appendix 5 in Section 10.5.3).

The 12-item MOS Sleep Scale assessment yields scores on six subscales (18, 21):

- Sleep Disturbance (4-item subscale on sleep initiation problems, and sleep maintenance problems).
- Snoring (single-item subscale).
- Shortness of Breath or Headache (single-item subscale asking about the frequency of awakening with shortness of breath or with a headache).
- Sleep Adequacy (2-item subscale asking about frequency of awakening fresh and rested in the morning and getting the amount of sleep needed).
- Daily Somnolence (3-item subscale).
- Sleep Quantity (single-item subscale representing the average number of hours slept).
- One Sleep Problems Index is also calculated based on 9 of the items.

Responses to all but the open-ended sleep quantity item are transformed to scores on a 0-100 metric, with higher item scores reflecting more of the attribute implied by the scale name. Scores on the multi-item subscales and indexes also range from 0 to 100.

The MOS Sleep will be completed by the patients at baseline and Week12.

8.1.6.4 WPAI

The WPAI is a 6-item validated questionnaire assessing the amount of absenteeism, presenteeism and daily activity impairment attributable to a specific health problem (WPAI:SHP version V2.0) (19). An adapted version of the WPAI:SHP will be used where the term PROBLEM was replaced by DIABETES, as requested by the authors.

The WPAI:Diabetes will be completed by the patients at baseline and Week 12.

8.2 SAFETY ASSESSMENTS

Planned time points for all safety assessments are provided in the SoA.

8.2.1 Physical examinations

A complete physical examination will include, at a minimum, assessments of the [Cardiovascular, Respiratory, Gastrointestinal and Neurological] systems. Height and weight will also be measured and recorded.

Investigators should pay special attention to clinical signs related to previous serious illnesses.

Any new finding or worsening of previous finding should be reported as a new AE.

8.2.2 Vital signs

Vital signs will be measured in a semi-supine position after 5 minutes rest and will include systolic and diastolic blood pressure and pulse.

Blood pressure (mmHg) should be measured when the patient is quiet and seated and with their arm outstretched in line with mid-sternum and supported. Measurement should be taken under standardized conditions, approximately at the same time of the day, on the same arm, with the same device and the values are to be recorded in the eCRF. Devices for blood pressure measurement should be regularly recalibrated according to manufacturers' instructions.

Heart rate (bpm) will be measured at the time of the measurement of blood pressure.

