1.3 SCHEDULE OF ACTIVITIES (SOA)

	Screening (weeks)	F	Run-in	(weeks	Intervention period (weeks)														Follow up	Notes	
Procedure	-6/-5	-4	-3	-2	-1		1	2	3	4	5	6	7	8	9	10	11	12	EOTC	2 to 4 days after last IMP dose	Visit Windows: Site visits: ±3 days Phone call visits: ±1 day relative to Visit 6
Visit ^a	1	2	3	4 2	5 2	6	7 2	8	9	10	11	12 2	13 2	14	15	16 2	17 2	18 ^b		19 ^d	
Day	-42/-35	-28	-20	-14	-7	1	7	14	21	28	35	42	48	56	64	71	78	84		86-88	
Informed consent	Х																				To be repeated in case of rescreening
Inclusion/Exclusion criteria	Х	Х	Х			Х															
Demography	Х																				
Full physical examination including height and weight	Х																				
Medical history	Х																				Medical, surgical and diabetes history
Method of mealtime insulin titration	Х					х															Current method at screening and the one to be followed during treatment period at randomization
Vital signs and body weight	Х					х								Х				х	х		Vital signs include heart rate and blood pressure (sitting position)
Dispensation/collection of study diary		Χ	Х			Х								Х	Х			Х	Х		

	Screening (weeks)					lr	nterve	entio	n per	riod (v	veeks)				Follow up	Notes				
Procedure	-6/-5	-4	-3	-2	-1		1	2	3	4	5	6	7	8	9	10	11	12	EOT ^C	2 to 4 days after last IMP dose	Visit Windows: Site visits: ±3 days Phone call visits: ±1 day relative to Visit 6
Visit ^a	1	2	3	4 2	5 2	6	7 2	8	9	10 2	11	12 2	13	14	15	16 2	17 2	18 ^b		19 ^d	
Day	-42/-35	-28	-20	-14	-7	1	7	14	21	28	35	42	48	56	64	71	78	84		86-88	
Dispensation of study intervention						Х								Х							
IMP compliance check														Х				Х	х		Collecting and counting used and unused pens
IRT call ^e	Х					Х								Х				Х	Х		
Randomization						Х															
Documentation and review of basal and mealtime insulin dose	Х	Х	Х			х	Х	Х	Х	Х	Х	Х	Х	Х	Х	х	х	Х	х		
Prior and concomitant medication	Х	Х	Х			Х					и			Х				Х	Х	Х	
CGM device dispensation ; blinded CGM and training including insertion of CGM sensor			X												х				х		If required, Investigators can arrange for patient's to attend the site after the first 10 days of CGM for the sensor to be replaced at the study site.
CGM recording ^f				20days											2	20 days	s	Х			

	Screening (weeks)	I	Run-in	(weeks	s)					lr	nterve	entio	n per	riod (v	veeks	s)				Follow up	Notes
Procedure	-6/-5	-4	-3	-2	-1		1	2	3	4	5	6	7	8	9	10	11	12	EOTC	2 to 4 days after last IMP dose	Visit Windows: Site visits: ±3 days Phone call visits: ±1 day relative to Visit 6

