2.1.4.4 Vital signs variables

Vital signs will be assessed according to the defined visit window (see Section 2.5.4).

The following vital signs will be assessed:

- Weight (Kg),
- Systolic blood pressure (mmHg) in sitting position,
- Diastolic blood pressure (mmHg) in sitting position,
- Heart rate (beats/min) in sitting position.

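### Protocol 8.2.2 gives two postures, semi-supine and seated, for the same blood pressure and pulse readings, while the Schedule of Activities and the SAP say sitting

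*Protocol*

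**What the plan says.** Protocol 8.2.2 starts with a general instruction, "Vital signs will be measured in a semi-supine position after 5 minutes rest", and lists systolic and diastolic pressure and pulse as the readings covered. The paragraph after it begins "Blood pressure (mmHg) should be measured when the patient is quiet and seated" and goes on to describe arm support. A standardization sentence follows: "Measurement should be taken under standardized conditions, approximately at the same time of the day, on the same arm, with the same device". The section closes with "Heart rate (bpm) will be measured at the time of the measurement of blood pressure".

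The note on the vital-signs row of the Schedule of Activities (Protocol 1.3) reads "Vital signs include heart rate and blood pressure (sitting position".

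SAP 2.1.4.4 defines the analysis variables as "Systolic blood pressure (mmHg) in sitting position" and "Diastolic blood pressure (mmHg) in sitting position", with heart rate defined in the same posture. SAP 2.4.5.5 plans summary statistics for all vital-sign variables, and for their changes from baseline, at baseline, Week 8 and Week 12 by treatment group.

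**The concern.** Section 8.2.2 is the detailed instruction that sites use to take these readings, and it cannot be followed as written. A site that obeys its first sentence departs from the second sentence and from the Schedule of Activities. A site that obeys those two departs from the first. The SAP expects about 50 sites, and each would have to settle the matter for itself.

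Two things are at stake. Semi-supine readings could be reported under variables defined as sitting. And a patient measured in one posture at baseline and in the other at Week 8 or Week 12 would show a change that partly reflects posture. Vital signs are among the few quantitative safety measures followed over time here: SAP 2.4.5.4 plans no laboratory analyses, and ECG is not applicable.

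**Working it through.** No sample size, power, margin or event count is involved, and the plan states no figure to reproduce. The check is a comparison of texts.

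| Place | Readings covered | Posture |
|---|---|---|
| Protocol 8.2.2, first sentence | systolic and diastolic pressure, pulse | semi-supine |
| Protocol 8.2.2, second sentence | blood pressure | seated |
| Protocol 8.2.2, last sentence | heart rate, taken with blood pressure | not named; follows blood pressure |
| Protocol 1.3, note on the vital-signs row | heart rate and blood pressure | sitting |
| SAP 2.1.4.4 | systolic and diastolic pressure, heart rate | sitting |
| SAP 2.1.1, vital signs at baseline | the same three | not named |
| SAP 2.4.5.5, summary by visit | all vital-sign variables | not named |

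1. **Are these different measurements with different postures?** No. The first sentence of 8.2.2 itself lists blood pressure and pulse, so it covers the same readings as the second and last sentences.

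2. **Which statement stands alone?** One place says semi-supine. Three say seated or sitting: the second sentence of 8.2.2, the Schedule of Activities note and SAP 2.1.4.4.

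3. **Does the standardization sentence settle it?** Not expressly. It asks for standardized conditions and spells out time of day, arm and device, but it does not name posture.

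4. **Does the SAP handle mixed posture?** No. Sections 2.1.4.4, 2.4.5.5 and the vital-sign windows in 2.5.4 give no rule for a reading taken in another posture.

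5. **What would mixed posture do to a change from baseline?** Let d be the average difference between a semi-supine and a sitting reading. A patient in the same posture at both visits has no false change, whichever posture it is; at worst the absolute values are mislabelled. A patient who moves from sitting to semi-supine gains d, and one who moves the other way loses d. If fractions p and q of patients move in these two directions, the mean change shifts by d × (p − q). The documents give none of d, p or q, so the shift cannot be evaluated, and its sign is unknown as well.

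**The case against.** The strongest reply is that the conflict is easy to resolve and has almost no consequence. The more specific sentence in 8.2.2 says seated and describes arm support. Heart rate goes with blood pressure, so every reading named in the general sentence is also covered by the seated one. The Schedule of Activities agrees, and Protocol section 8 treats adherence to that schedule as mandatory. A false change within a patient would need a change of posture between visits, despite the call for standardized conditions. Vital signs are not among the safety endpoints listed in Protocol Table 1 or SAP 2.1.4, Protocol Table 8 gives no analysis for them, and SAP 2.4.5 describes the safety analysis as essentially descriptive.

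Most of this stands. It lowers the chance of mixed posture and limits the consequence. It does not remove the contradiction, because no passage says which sentence of 8.2.2 prevails.

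Three stronger readings are tempting, and the documents do not support them:

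- **A numerical shift in mean blood pressure.** A reader might assume a 5 mmHg posture effect and 20% of patients switching, and infer a shift of 0.20 × 5 = 1 mmHg. Both inputs are unsourced, and the product needs every switch to go the same way. With 10% switching each way, the same formula gives 5 × (0.10 − 0.10) = 0.
- **A change-from-baseline table that carries a sitting label.** The posture is in the variable definitions of SAP 2.1.4.4. SAP 2.4.5.5, which specifies the summary, names none; a table label would be an inference from the definitions.
- **A biased comparison of the arms.** Allocation is randomized 1:1, and nothing in the documents links posture to treatment.

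**Conclusion.** The point holds as a minor internal inconsistency. Section 8.2.2 assigns two postures to the same readings, and its first sentence conflicts with the Schedule of Activities and the SAP. The possible harm is extra noise and mislabelled values in a descriptive safety summary. No test, margin, listed endpoint or numerical eligibility threshold depends on these readings.

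The size is unknown and is left unstated, since it would rest on a posture effect and a switching pattern that the documents do not give. The expectation of no between-arm bias assumes that the posture a site uses does not depend on the treatment assigned. Whether any reading was actually taken semi-supine cannot be told from the protocol and SAP.

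**What to change.** In the first sentence of Protocol 8.2.2, replace semi-supine with sitting, so that the section agrees with its own second sentence, the Schedule of Activities and SAP 2.1.4.4. An amendment or a site clarification note would do.

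The protocol is dated 31 May 2019 and the SAP 1 July 2021, so some readings may already exist, and a wording change cannot correct those. If any were taken in another posture, state this in the report and do not label them as sitting.

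The cost is one word and, where needed, a sentence in the report. It adds no visit, procedure or analysis.
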